3.0 BACKGROUND AND RATIONALE

3.1 Clinical course of CLL.

CLL is the most common leukemia in the United States and Western hemisphere.(2) There is remarkable clinical diversity in patients with CLL. Following diagnosis, some patients have smoldering, asymptomatic disease that may not progress for many years, others are diagnosed with advanced stage and still others are diagnosed with early stage disease that rapidly progresses, causing symptoms and/or bone marrow failure and require treatment. Wierda et al. developed a nomogram designed to predict the time to first treatment for previously untreated CLL patients who did not have an indication for treatment at their initial assessment.(3) Patients with increased cervical lymph node size, unmutated *IGHV* gene, elevated LDH, ≥3 involved lymph node sites, del(11q) or del(17p) demonstrated more rapid disease progression, with shorter time-to-first-treatment.(3)

3.2 Studies of early versus deferred treatment in CLL.

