No study has demonstrated a survival benefit for early versus deferred treatment in CLL, although the initial studies were done with alkylating agent-based treatment, which would be considered ineffective given current standards of care. Also, historic trials included all patients and did not have reliable tools to screen out low-risk patients who may never need treatment. Two large French studies definitively demonstrated a lack of survival benefit for early versus deferred treatment with chlorambucil monotherapy,(4) while a large meta-analysis also showed no survival benefit for early treatment with either chlorambucil or anthracycline-based chemotherapy.(5) More recently, a German-French co-operative study showed event-free survival, but not overall survival benefit for early treatment with FCR, although follow-up was short.(6) Given the lack of demonstrable survival benefit with early therapy, early-stage CLL is managed with "watchful waiting". Patients are considered for treatment only if significant disease-related symptoms or marrow failure develop.(7) The lack of survival benefit seen in early therapy studies, despite prolonged PFS, also relates to a combination of toxicity from chemotherapy, as well as inability to eradicate the CLL clone with the result that the disease is less treatment-sensitive at relapse. Therefore, these older trials lacked our current understanding of high-risk features, including low-risk patients, and utilized ineffective therapies, which probably contributed to the negative findings.

3.3 Early-stage CLL is associated with increased infection risk and a higher incidence of other cancers.

Even untreated, early stage CLL or its precursor condition, monoclonal B-cell lymphocytosis (MBL), are associated with significant infection risk(8, 9) and infection remains a leading cause of morbidity and mortality in CLL. In addition, there is an increased incidence of other hematologic(10, 11) and non-hematologic cancers(12, 13) in patients with even early-stage CLL or high-count MBL. Treatment with a non-immunosuppressive, non-genotoxic agent, may potentially reduce these risks.

3.4 Adverse effects of chemotherapy-based treatment in CLL.

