Patients with CLL have a higher risk of second cancers, particularly skin, AML/MDS and Richter transformation.(14) While the impact of specific therapy is controversial, it was suggested that fludarabine-based treatment may increase the risk of Richter transformation(15) (and [name], unpublished data). Fludarabine-based chemotherapy is also associated with myelosuppression, lymphocyte depletion, and infection risk.(16) Therefore, delay of initiation of chemoimmunotherapy is a desirable goal. Early studies were conducted prior to the availability of highly-effective, non-myelosuppressive and non-mutagenic agents, such as ibrutinib. Although data is currently lacking, early treatment with ibrutinib could reasonably be expected to result in a lower incidence of both treatment-related infectious complications and second cancers relative to chemoimmunotherapy.

3.5 Ibrutinib as first-line therapy in CLL.

lbrutinib demonstrated remarkable efficacy in first-line treatment of CLL in elderly patients.(17) Treatment was well tolerated, with few serious adverse events. Mild diarrhea was the most common adverse event,(17) but generally self-limited. Grade 3 toxicity requiring temporary treatment interruption was seen in 29% of patients, but no patient permanently ceased treatment due to toxicity. Of 31 patients, with a median follow-up of 22 months, only 1 patient progressed; this patient, who had del(17p), developed Richter transformation after approximately 6 months on treatment. In this study 96% remained progression-free at 24 months. More recently, the RESONATE-2 study demonstrated a survival benefit relative to chlorambucil and an impressive 90% PFS at 18 months, leading to first line approval of ibrutinib by the U.S. Food and Drug Administration. Rare, but serious adverse events include atrial fibrillation, which occurred in approximately 6% of patients in the ibrutinib arm; minor bleeding is more common in ibrutinib-treated patients, but major bleeding is rare.(18) An update of this study at ASH 2016 demonstrated increasing rate of CR/CRi over time and 89%

PFS at 24 months, with 79% of patients remaining on therapy at a median follow-up of 28.5 months.(19)

3.6 Resistance to ibrutinib therapy.

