4.0 STUDY POPULATION

4.1 Inclusion criteria.

- 1. Diagnosis of CLL/SLL that meets IWCLL diagnostic criteria.(7)
- Patients must be aged over 18 years at the time of informed consent, understand and voluntarily sign an informed consent, and be able to comply with study procedures and follow-up examinations.
- 3. No treatment indication according to IWCLL criteria.(7)
- 4. Estimated time to first treatment of 3 years or less according to MDACC nomogram.(3)
- 5. ECOG performance status of 0-2.(27)
- 6. Male and female subjects who agree to use both a highly effective method of birth control (e.g., implants, injectables, combined oral contraceptives, some intrauterine devices [IUDs], complete abstinence¹, or sterilized partner) and a barrier method (e.g., condoms, vaginal ring, sponge, etc.) during the period of therapy and for 30 days after the last dose of study drug for females and 90 days for males. OR Female subjects who are of non-reproductive potential (i.e., postmenopausal by history no menses for ≥1 year; OR history of hysterectomy; OR history of bilateral tubal ligation; OR history of bilateral oophorectomy).
- 7. Adequate hepatic and renal function as indicated by all of the following: Total bilirubin </=1.5 x institutional Upper Limit of Normal (ULN) except for patients with bilirubin elevation due to Gilbert's disease or of non-hepatic origin who will be allowed to participate; an ALT </=2.5 x ULN; and estimated creatinine clearance

About HMA/Working Groups/CTFG/2014 09 HMA CTFG Contraception.pdf

Protocol 2017-0039. Ibrutinib early treatment for high-risk CLL. Version 11, 19Dec2022

Page 8 of 43

¹ Complete abstinence is a highly effective method only if defined as refraining from heterosexual intercourse during the entire period of risk associated with the study treatments. The reliability of sexual abstinence needs to be evaluated in relation to the duration of the clinical trial and the preferred and usual lifestyle of the subject. http://www.hma.eu/fileadmin/dateien/Human_Medicines/01

- (CrCl) of > 30 mL/min, as calculated by the Cockroft- Gault equation unless disease related.
- 8. PT/INR <1.5 x ULN and PTT (aPTT) <1.5 x ULN (unless abnormalities are unrelated to coagulopathy or bleeding disorder).

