 - A decrease in lymph node size by 50% or more either in the sum products of up to 6 lymph nodes, or in the largest diameter of the enlarged lymph node(s) detected prior to therapy.
 - No increase in any lymph node, and no new enlarged lymph node. In small lymph nodes (</=2 cm), an increase of less than 25% is not considered to be significant.
- 3. A reduction in the noted pretreatment enlargement of the spleen or liver by 50% or more, as detected by CT scan.
- 4. The blood count should show one or more of the following results:
 - Neutrophils more than 1, without need for exogenous growth factors.
 - Platelet counts greater than 100 x10⁹/L (100 000/μL) or 50% improvement over baseline without need for exogenous growth factors.
 - Hemoglobin greater than 110 g/L (11.0 g/dL) or 50% improvement over baseline without requiring red blood cell transfusions or exogenous erythropoietin.

Criteria for Stable Disease:

Stable disease is defined as not meeting criteria for complete remission, partial remission or progressive disease.

Criteria for Progressive Disease:

Progressive disease during or after therapy is characterized by at least one of the following:

- Lymphadenopathy. Appearance of any new lesion (>1.5cm) or increase by 50% or more in greatest determined diameter of any previous site.
- 2. An increase in the previously noted enlargement of the liver or spleen by 50% or more or the de novo appearance of hepatomegaly or splenomegaly.
- 3. An increase in the number of blood lymphocytes by 50% or more with at least 5000 B lymphocytes per microliter.
- 4. Occurrence of cytopenia (neutropenia, anemia, or thrombocytopenia) attributable to CLL.
- 5. After treatment, the progression of any cytopenia (unrelated to autoimmune cytopenia), as documented by a decrease of HGB levels by more than 20 g/L (2 g/dL) or to less than 100 g/L (10 g/dL), or by a decrease of platelet counts by more than 50% or to less than 100 x 10^9/L (100 000/μL), which occurs at least 3 months after treatment, defines disease progression, if the marrow biopsy demonstrates an infiltrate of clonal CLL cells.

Minimal residual disease (MRD) analysis.

MRD will be assessed in bone marrow after 6, 12, and 24 months, using a standardized 4-color flow cytometry assay, with a sensitivity of 0.01%.(28) Patients will be categorized as MRD-negative or MRD-positive.

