15.0 STATISTICAL CONSIDERATIONS

- **15.1** This is a phase II single arm study of ibrutinib monotherapy in early stage CLL with a predicted time-to-treatment interval of less than 3 years, according to the MDACC nomogram developed by Wierda et al.(4) The primary objective is to evaluate the CR/CRi rate at two years. A maximum of 50 patients will be enrolled in the study with an estimated accrual rate of 4 patients per month; the accrual duration will be approximately 1 year.
- **15.2** The historical CR/CRi rate for patients who are treated when they have symptomatic disease requiring therapy, in the first line setting is 16% at 2 years (Pharmacyclics, internal data). We expect that early therapy with ibrutinib may increase this CR/CRi rate at two years from 16% to 30%. A sample size of 50 patients achieves 78% power to detect a difference of 14% in the 2-yr complete remission rate (i.e. to double the remission rate) using a one-sided binomial test. The target significance level is 0.05. These results assume that the population proportion under the null hypothesis is 16%.
- **15.3** For the primary analysis, we will calculate the proportion of patients with CR/CRi at 24 months, along with 95% confidence intervals. We will test the observed 2-year rate versus the null hypothesis of a 16% rate using a one-sided exact binomial test.
- 15.4 For secondary analyses, proportions of patients with objective response at 6, 12 and 24 months and CR/CRi at 6 and 12 months will be estimated along with 95% confidence intervals. The Kaplan-Meier method will be applied to estimate the progression free survival (PFS), the time to best response, the time to CR/CRi and time-to-alternative treatment survival curves. We will calculate the median time as well as the 2-year and 5-year survival rate and the corresponding 95% confidence intervals. In addition, we will directly compare the observed PFS time to each patient's individual predicted PFS time.

Protocol Amendments

Any amendments to the Protocol or Informed Consent Form must be sent to Pharmacyclics for review and approval prior to submission to the IRB. Written verification of IRB approval will be obtained before any amendment is implemented.

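### Section 15.4 compares observed PFS with a predicted PFS that the documents never supply; the only individual prediction is time to first treatment, and a direct comparison of times does not handle censoring

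*Combined protocol and SAP*

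**What the plan says.** Section 15.4 plans Kaplan-Meier curves for PFS, time to best response, time to CR/CRi and time to alternative treatment, with medians and 2-year and 5-year rates. It then adds that "we will directly compare the observed PFS time to each patient's individual predicted PFS time". It names no method, summary measure, data cut or treatment of censored patients for that comparison.

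The documents describe one patient-level prediction, and each time as time to treatment:

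- Section 3.1 introduces "a nomogram designed to predict the time to first treatment for previously untreated CLL patients" who had no treatment indication at first assessment.
- Section 4.1 item 4 requires "Estimated time to first treatment of 3 years or less according to MDACC nomogram".
- Section 15.1 describes the population as having "a predicted time-to-treatment interval of less than 3 years, according to the MDACC nomogram". (The reference number given there, 4, is a chlorambucil trial; the nomogram paper is reference 3.)

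PFS at 2 years is secondary endpoint 1 and time to alternative treatment is secondary endpoint 4 (section 1.2). Progressive disease is defined in section 11.0.

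**The concern.** The comparison cannot be carried out as written, because one of its two quantities does not exist in the documents. If the nomogram value is put in its place, two different events are compared: the start of first therapy in an untreated patient, and progression in a patient who has received ibrutinib.

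A direct comparison of times also needs an observed time for each patient. Most patients will have only a censored one, and a difference computed from censored times grows as follow-up lengthens, whatever the drug does.

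In a single-arm trial of early treatment, a statement that patients did better than predicted is easily quoted. Here the comparator, the data cut and the handling of censoring would all be settled after the data are seen.

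**Working it through.** **The plan's own figure.** This comparison has none. The nearest stated figure is the primary power in 15.2, and it holds: with n = 50 and rejection at 13 or more CR/CRi, the exact one-sided level at 16% is 0.0475 and the power at 30% is 0.777, against the stated 78%. Nothing below affects it.

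**Step 1: the events.** Section 3.2 says of untreated early disease that "Patients are considered for treatment only if significant disease-related symptoms or marrow failure develop". Section 11.0 counts as progression "Appearance of any new lesion (>1.5cm) or increase by 50% or more in greatest determined diameter of any previous site". It also counts a 50% rise in blood lymphocytes with at least 5000 B cells per microlitre (section 6.7 sets drug-related lymphocytosis aside). Neither requires a treatment indication. The definitions overlap in part: cytopenia attributable to CLL is progression in section 11.0 and is close to the marrow failure of section 3.2. The difference in events remains at any length of follow-up.

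**Step 2: how many times are censored.** Inputs: N = 50 (15.1); 24-month PFS of 96% and 89% in the two first-line studies in 3.5. Applying these to patients without a treatment indication is an assumption.

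- Events by 24 months: 50 × (1 - 0.96) = 2.0 and 50 × (1 - 0.89) = 5.5.
- Event-free at 24 months: 48 and 44.5.

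**Step 3: what a mean difference would show.** Assume a constant hazard h = -ln(S24)/24, including after study treatment ends at 2 years, and predictions spread evenly over a range. The documents give only the 36-month cap, so three ranges are shown. If censored times are used as observed times, the mean observed time at a common cut c is (1 - exp(-hc))/h:

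- 89% PFS: h = 0.00486 per month; means 22.65, 33.03 and 52.05 months at c = 24, 36 and 60.
- 96% PFS: h = 0.00170 per month; means 23.52, 34.92 and 57.04 months.

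Mean predictions are 21, 24 and 30 months for ranges 6-36, 12-36 and 24-36. Mean observed minus predicted, in months:

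| PFS at 24 months | Predictions | Cut 24 | Cut 36 | Cut 60 |
|---|---|---|---|---|
| 89% | 6-36 | +1.65 | +12.0 | +31 |
| 89% | 12-36 | -1.35 | +9.0 | +28 |
| 89% | 24-36 | -7.35 | +3.0 | +22 |
| 96% | 6-36 | +2.5 | +13.9 | +36 |
| 96% | 12-36 | -0.5 | +10.9 | +33 |
| 96% | 24-36 | -6.5 | +4.9 | +27 |

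At 89% PFS, moving the cut from 24 to 60 months with the hazard unchanged shifts the mean by 52.05 - 22.65 = 29.4 months. At a fixed 24-month cut, going from 89% to 96% PFS shifts it by only 23.52 - 22.65 = 0.87 months. The cut dominates.

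**Step 4: classifying patients as longer or shorter than predicted.** A patient censored before the predicted time cannot be classified. At a 24-month cut with predictions of 12-36 months, half the predictions exceed 24, so 50 × 0.89 × 0.5, about 22 patients, are unresolved. Once everyone has 36 months of follow-up the number is 0, because no prediction exceeds 36.

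**The case against.** The sentence promises only a comparison. A plot of observed against predicted time with censored times marked would satisfy it, and Kaplan-Meier is named for PFS in the same paragraph. The plan promises neither a mean difference nor a share of patients beating their prediction. This stands: Step 3 shows what the most literal summary would do, not what the plan says will be reported.

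A reader might go further and infer that the same data would yield very different shares of patients doing better than predicted. At a 24-month cut with 89% PFS and predictions of 12-36 months, the share would be 46% if censored times are taken as event times, 12% among patients with events only, and 90% if censored patients count as longer. The documents do not support that as a description of this plan. They name no such share, and the first two rules are poor practice that nothing in the plan proposes. At 36 months the first and third rules agree at 89%; only the events-only rule (32%) departs. With 5-year rates planned in 15.4 and follow-up beyond 2 years in 5.3, the ambiguity belongs mainly to early cuts.

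Nor do the documents support the inference that the comparison would run against the drug at an early cut. The sign at 24 months depends on the unknown spread of predictions: at 89% PFS it is negative only if the mean prediction exceeds 22.65 months.

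The label is probably a loose name for the nomogram value. That explains the sentence, but it does not make the two events the same.

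**Conclusion.** The concern holds as a minor point, and the sentence is wrong as written rather than merely short on detail. No predicted PFS exists in the documents, and the prediction that does exist is for a different, partly overlapping event. That part rests on the text alone.

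The censoring part rests on assumptions: 24-month PFS of 89% to 96% carried over from first-line studies, a constant hazard and an assumed spread of predictions. Under them, 2 to 5.5 of 50 patients have an event by 24 months. In every scenario shown, a mean observed-minus-predicted time rises with follow-up, from -1.35 to +28 months between the 24-month and 60-month cuts in the central illustration.

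The reach is limited. This is one descriptive secondary analysis; it is not a listed endpoint and no hypothesis in section 2.0 depends on it. The primary CR/CRi test and the Kaplan-Meier PFS estimates are unaffected.

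**What to change.** In 15.4, replace the predicted PFS time with the nomogram-predicted time to first treatment. Replace the direct comparison of times with a descriptive, censoring-aware one at a stated horizon. There are two ways to do this:

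- Preferably, set the Kaplan-Meier curve of time to alternative CLL treatment (secondary endpoint 4, the closest available event) against the average nomogram-predicted curve.
- Alternatively, report observed over expected events with a 95% confidence interval.

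If PFS is kept as the observed endpoint, say that the events differ. In either case, state that the comparison is not like for like: all patients have received ibrutinib, and alternative treatment may follow toxicity. Section 2.0 expects 10-15% to stop for toxicity, which is 5 to 7.5 of 50, though not all of them would start another therapy.

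Do not censor remote patients at progression, since that removes them just when alternative treatment becomes likely. Section 5.3 ends telephone calls at progression, while 12.1.8 refers to post-progression follow-up. Reconcile the two, or count progression as an event in remote patients.

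The cost is wording, provided each patient's nomogram prediction was stored. If it was not, recalculation needs the nomogram's weights, which the documents do not give.

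The observed/expected ratio also needs an assumed hazard shape, as does the average predicted curve if only a single time per patient was kept. Under an exponential shape, reading the value as a mean instead of a median raises expected events by 1/ln 2 - 1 = 44%. At 24 months, with 89% PFS times standing in for follow-up and predictions of 12-36 months:

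- Mean reading: 50 × 22.65 × ln(36/12)/24 = about 52 expected events.
- Median reading: 52 × ln 2 = about 36.

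The expected count can therefore pass 50 even at a 24-month horizon, which is a further reason to prefer the two curves.
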